4. Study Population

Inclusion Criteria

- Age \geq 18 years
- ASA physical status I-II
- Voluntary participation with signed informed consent
- Living kidney donor scheduled for elective donor nephrectomy

Exclusion Criteria

- Diabetes mellitus diagnosis
 - Development of postoperative delirium
 - Known psychiatric illness or psychiatric medication use
 - Neurological or musculoskeletal disorders
 - Chronic pain or chronic pain treatment
 - Recent significant psychological trauma
 - Analgesic drug use within the last month
-

5. Interventions

Intervention Group: Preoperative Psychiatric Consultation

Participants received a standardized 15-minute psychiatric session one hour before surgery under psychiatrist supervision, including:

- History-taking (3–5 minutes)
- Psychoeducation regarding anxiety and surgical preparation (3–5 minutes)
- Diaphragmatic breathing exercises (1–3 minutes)
- Guided imagery techniques (3–5 minutes)

The intervention was delivered by an anesthesiologist trained by a psychiatrist through structured educational sessions.

Control Group: Standard Preoperative Care

Participants received routine preoperative evaluation. No psychiatric intervention was performed.

6. Outcome Measures

Primary Outcome

- Postoperative Pain Score (VAS 0–10)**

Time Frame: Postoperative 30 minutes, 2 hours, 6 hours, 12 hours, 24 hours, and 48 hours.

Secondary Outcomes

- State Anxiety Score (Beck Anxiety Inventory, 0–63)**

Time Frame: 30 minutes preoperatively, postoperative 24 hours, postoperative 48 hours.

- Postoperative SpO₂ Levels (%)**

Time Frame: Postoperative 30 minutes, 2 hours, 6 hours, 12 hours, 24 hours, 48 hours.

- Intraoperative Heart Rate (beats/min)**

Time Frame: Pre-induction, 30 minutes after induction, 1 hour after induction.

- Intraoperative SpO₂ Levels (%)**

Time Frame: Pre-induction, 30 minutes after induction, 1 hour after induction.

- Intraoperative Systolic Blood Pressure (mmHg)**

Time Frame: Pre-induction, 30 minutes after induction, 1 hour after induction.

- Intraoperative Diastolic Blood Pressure (mmHg)**

Time Frame: Pre-induction, 30 minutes after induction, 1 hour after induction.

- Total Opioid Consumption (mg)**

Time Frame: Intraoperative period and postoperative first 24 hours.

- Antiemetic Use (Yes/No, mg)**

Time Frame: Intraoperative period and postoperative first 6 hours.

7. Data Collection Procedures

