Data will be collected at standardized time points by trained staff members. Hemodynamic parameters will be retrieved from anesthesia monitoring records. Pain scores will be evaluated using a 10 cm Visual Analog Scale. Anxiety assessments will be performed by a blinded outcomes assessor.

8. Statistical Analysis Plan

- Categorical variables: χ^2 or Fisher's exact test
- Continuous variables with normal distribution: Independent samples t-test
- Non-normal distribution: Mann-Whitney U test
- Repeated measurements: Repeated Measures ANOVA or Friedman test
- Correlations: Pearson or Spearman coefficients
- Significance threshold: $p < 0.05$
- Software: SPSS 15.0 version

All analyses will be performed per-protocol.

9. Ethical Considerations

- Ethics Committee Approval: **Akdeniz University Clinical Research Ethics Committee**
Approval Number: **2023-KAEK-20 / 840**
- Board Status: Approved
- Participation is voluntary; written informed consent obtained from all donors.
- No investigational drug or device used.
- Risks are minimal and limited to standard perioperative care.

10. Study Timeline

- Start of enrollment: November 1, 2023
- Primary completion: October 1, 2024
- Study completion: November 1, 2024

11. Data Management and Monitoring

A formal Data Monitoring Committee is not required due to minimal-risk behavioral intervention and absence of investigational medicinal products.

All data will be anonymized and stored securely following institutional data protection guidelines.

12. Publication Plan

Findings will be submitted to peer-reviewed anesthesiology and transplant journals and may be presented at national and international conferences.

13. References

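### Section 8 compares the arms only with unadjusted tests; a prespecified pre-allocation covariate would be a cheap gain in precision for heart rate and blood pressure, and a modest or nil one for pain

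*Combined protocol and SAP*

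**What the plan says.** Section 8 (Statistical Analysis Plan) gives one line per type of variable. Categorical outcomes get a chi-square test "or Fisher's exact test". Continuous outcomes get "Continuous variables with normal distribution: Independent samples t-test" or, failing normality, "Non-normal distribution: Mann-Whitney U test". Serial outcomes get "Repeated measurements: Repeated Measures ANOVA or Friedman test". The last analysis listed is "Correlations: Pearson or Spearman coefficients", which describes association and does not adjust the arm comparison. No ANCOVA, regression model, stratified test or covariate appears anywhere.

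Section 3 places randomisation, by sealed envelopes, at the preoperative evaluation and names no stratification, blocking or minimisation factor.

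The places that bear on possible covariates are these:

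- Section 4 sets an age limit and "ASA physical status I-II" as inclusion criteria, so age and ASA class are known before allocation.
- Section 5 says of controls "Participants received routine preoperative evaluation". It does not say what that evaluation records. The intervention is a 15-minute session one hour before surgery.
- Section 6 gives the intraoperative heart rate and blood pressure outcomes as "Time Frame: Pre-induction, 30 minutes after induction, 1 hour after induction". The first Beck Anxiety Inventory (BAI) is 30 minutes before surgery, and the first pain score is 30 minutes after it.
- Section 7 takes hemodynamic data from the anesthesia monitoring records.

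**The concern.** Donors differ in usual heart rate and blood pressure, and may differ in pain by age or physical status. Nothing in the design balances these characteristics and nothing in the analysis uses them, so the variation they explain counts as noise. Sections 3 to 8 state no sample size, and section 10 allows 11 months from first enrolment to primary completion, so ample precision cannot be taken for granted.

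There is also a timing issue for anyone who decides to adjust. The plan lists no measurement of any outcome before the session. The readings that look most like baselines, the pre-induction vital signs and the preoperative BAI, come after the session and may already carry its effect. A plan that adds covariates must therefore say which readings are excluded.

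**Working it through.** **What the documents supply.** They give no sample size, effect size, SD or covariate-outcome correlation, so there is no figure of the plan's own to reproduce. Everything below is assumed: two-sided alpha 0.05 (section 8 gives 0.05 without sidedness), 1:1 allocation, 20-40 donors per arm, a 0.5 SD effect for power, and a range of correlations.

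**Formulas.** Let N be the total number of donors, k the number of covariates and R² the share of outcome variance they explain (r² for a single covariate).

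- Gross variance ratio, adjusted to unadjusted: 1 − R².
- Expected cost of estimating k covariates: a factor of 1 + k/(N − k − 3).
- Net variance ratio: (1 − R²) × [1 + k/(N − k − 3)].

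**Cost if the covariates predict nothing.**

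| Donors per arm | k = 1 | k = 2 |
|---|---|---|
| 20 (N = 40) | 1/36 = 2.8% | 2/35 = 5.7% |
| 30 (N = 60) | 1/56 = 1.8% | 2/55 = 3.6% |
| 40 (N = 80) | 1/76 = 1.3% | 2/75 = 2.7% |

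The cost is therefore about 1-6% of variance for one or two covariates.

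**Heart rate, systolic and diastolic pressure: one same-variable covariate, assumed r = 0.3-0.6.**

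- 20 per arm: 0.91 × 1.028 = 0.935 and 0.64 × 1.028 = 0.658, a net fall of 6-34%.
- 40 per arm: 0.91 × 1.013 = 0.922 and 0.64 × 1.013 = 0.648, a net fall of 8-35%.
- Two-sample t power at 40 per arm and 0.5 SD is 59.8% unadjusted. With the net variances above and one degree of freedom fewer, it is 63.3% at r = 0.3 and 78.3% at r = 0.6.

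**VAS pain: age and two-level ASA class (k = 2), assumed multiple correlation 0.1-0.3.** Net variance ratios (below 1 is a gain):

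| Donors per arm | R² = 0.01 | R² = 0.04 | R² = 0.09 |
|---|---|---|---|
| 20 | 1.047 | 1.015 | 0.962 |
| 30 | 1.026 | 0.995 | 0.943 |
| 40 | 1.016 | 0.986 | 0.934 |

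With age alone (k = 1) and R² = 0.04 the ratios are 0.96 × 1.028 = 0.987, 0.96 × 1.018 = 0.977 and 0.96 × 1.013 = 0.973. The result for pain runs from a small loss to a gain of about 7%.

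**Validity of the planned test.** In 20,000 simulated trials per setting with 30 per arm, no true effect and a prognostic covariate at r = 0.2, 0.5 or 0.7, the unadjusted t-test rejected in 5.1%, 4.9% and 5.0%. Its error rate is correct.

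**Why the post-session readings must be barred.** Suppose the session shifts the pre-induction reading by a SD, that reading has slope 0.6 on the later one, and the total effect is 0.5 SD. Adjusting for the pre-induction reading then estimates 0.5 − 0.6a: 0.5 − 0.18 = 0.32 SD at a = 0.3, and 0.5 − 0.30 = 0.20 SD at a = 0.5. Simulation at 30 per arm gave the same values.

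**The case against.** The strongest reply is that an unadjusted comparison in a randomised trial is a legitimate choice. That stands: the error rate is correct and the estimate is unbiased.

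It also stands that the larger gains concern secondary outcomes and depend on a covariate that the documents do not list. Because the envelopes are used during the preoperative evaluation, even a reading from that visit is not shown to precede allocation. For the primary outcome, the documented covariates are age and a two-level ASA class, in donors already selected for ASA I-II and no chronic pain. No document says that either predicts pain. The missing sample size does not show that the trial is small, and it equally prevents calling the cost of covariates negligible.

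Three stronger readings are tempting and unsupported:

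- A reader might infer that resting heart rate and blood pressure are already available for adjustment. They may be, but the earliest listed reading is pre-induction.
- A reader might count chance imbalance as a second harm beside the loss of precision. At 40 per arm the 95% limit for a baseline gap is 1.96 × √(2/40) = 0.44 SD, of which 0.13-0.26 SD carries into the outcome at r = 0.3-0.6. The unadjusted standard error already includes this, so it is the same loss seen another way.
- A reader might infer that the plan biases its result by adjusting for post-session values. Section 8 proposes no such adjustment; the point matters only as a guard once covariates are added.

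What survives is that a better-specified analysis is available at little cost and the plan does not use it.

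**Conclusion.** The point holds as an efficiency weakness and a cheap improvement. No planned arm comparison uses a covariate, no stratification factor is stated, and at least age and ASA class are known before allocation. The consequence is wider intervals than necessary. It is not bias or an invalid test.

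The size differs by outcome. For heart rate and blood pressure, about 6-35% of the variance could be removed net of degrees of freedom, if r is 0.3-0.6, the trial has 20-40 per arm, and a true pre-allocation reading exists. For pain the expected gain is modest, and at 20-30 per arm it may be nil or slightly negative. All of these figures rest on assumed inputs.

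**What to change.** Amend section 8 as follows, with covariates fixed before the data are examined.

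1. **Heart rate, systolic and diastolic pressure at 30 minutes and 1 hour after induction:** ANCOVA or a linear mixed model with arm and the same variable from the routine preoperative evaluation. Copy that reading to the case record before the envelope is opened, and add it to sections 6 and 7 as collected data. For donors already enrolled, only a reading shown to precede allocation qualifies.
2. **VAS pain:** the same type of model with arm and age, adding ASA class if numbers allow.
3. **Excluded covariates:** state that the pre-induction readings and the 30-minute preoperative BAI follow the session and are not to be used for adjustment. They remain outcomes.
4. **Non-normal outcomes:** use rank-based ANCOVA where the outcome is clearly non-normal, which is possible for a bounded 0-10 scale.
5. **Sensitivity analysis:** keep the planned t-test or Mann-Whitney test.

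The cost is SAP wording, one set of vital signs to copy per donor, and about 1-6% of variance for one or two covariates that turn out to predict nothing.

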Study Protocol

Preoperative Psychotherapy and Its Effects on Anxiety, Hemodynamics, and Pain in Living Kidney Donors (PREPSY-KD)

Protocol Version: 1.0

Protocol Date: November 2023

Organization's Protocol ID: KAEK-840

1. Background and Rationale

Living kidney donation is an essential treatment modality for end-stage renal disease (ESRD). Donor nephrectomy, while performed in healthy individuals, is associated with significant psychological stress due to hospitalization, surgical anticipation, anesthesia concerns, and uncertainty regarding recovery. Preoperative anxiety has been shown to negatively affect postoperative pain, hemodynamic stability, anesthetic requirements, and overall recovery.

Psychotherapeutic interventions such as psychoeducation, guided imagery, and diaphragmatic breathing exercises have demonstrated benefits in reducing perioperative anxiety and improving physiological parameters. However, there is limited prospective evidence evaluating the effect of structured preoperative psychiatric consultations on anxiety, hemodynamic responses, and postoperative pain in living kidney donors.

This study aims to assess whether a brief standardized psychiatric consultation administered before donor nephrectomy affects perioperative anxiety levels, intraoperative hemodynamics, and postoperative pain outcomes.

2. Study Objectives

Primary Objective

- To evaluate the effect of preoperative psychiatric consultation on postoperative pain scores measured via the Visual Analog Scale (VAS) at predefined postoperative time points.

Secondary Objectives

- To compare preoperative and postoperative anxiety levels between intervention and control groups using the Beck Anxiety Inventory (BAI).
 - To compare intraoperative hemodynamic parameters (heart rate, systolic and diastolic blood pressure, SpO₂) between groups.
 - To evaluate postoperative oxygen saturation trends.
 - To assess postoperative opioid consumption and antiemetic requirements.
-

3. Study Design

- **Study Type:** Interventional

- **Design:** Prospective, randomized, parallel-assignment clinical trial
- **Number of Arms:** 2 (Intervention vs. Standard Care)
- **Masking:** Single-blind (Outcomes Assessor)
- **Allocation:** Randomized
- **Primary Purpose:** Supportive Care
- **Study Duration:** November 2023 – November 2024

Randomization was performed via sealed envelopes during preoperative evaluation. Outcome assessors evaluating VAS scores were blinded to group allocation.

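### If the repeated-measurements line of section 8 is applied to VAS, a donor missing any one of the six readings drops out of that analysis with all their other scores, and the plan has no rule to prevent it

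*Combined protocol and SAP*

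**What the plan says.** Section 2 sets the primary objective on "postoperative pain scores measured via the Visual Analog Scale (VAS) at predefined postoperative time points" and names no single time as primary. Section 6 fixes the schedule: "Time Frame: Postoperative 30 minutes, 2 hours, 6 hours, 12 hours, 24 hours, and 48 hours". Postoperative SpO₂ is read at the same six times, and the Beck Anxiety Inventory (BAI) at three.

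Section 8 has one line for data of this kind: "Repeated measurements: Repeated Measures ANOVA or Friedman test". It does not say that arm enters as a between-donor factor. The same section lists tests for a single continuous variable: "Continuous variables with normal distribution: Independent samples t-test", with Mann-Whitney U when the distribution is not normal. It does not say which of these lines governs VAS. It closes with "All analyses will be performed per-protocol", and per-protocol is not defined.

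No section covers missed readings, imputation, withdrawal, discharge before 48 h, or use of all available data.

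**The concern.** Classical repeated-measures ANOVA and the Friedman test work on complete rows. A donor with five of six VAS scores contributes nothing to either. This comes from the methods themselves, so it would happen even if every randomised donor were in the analysis set.

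Two things are at stake. Gaps unrelated to pain waste scores already recorded and cost power. Gaps related to pain leave complete cases that no longer represent the two arms equally, so a between-arm difference from repeated-measures ANOVA can be distorted. Friedman raises a different problem: it compares times within donors and has no arm factor, so it does not answer the primary objective at all.

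**Working it through.** The plan states no sample size, power, SD, effect size or missing-data rate, so there is no figure of its own to reproduce. From the documents come the number of readings (six for VAS and SpO₂, three for BAI) and the named methods. All rates and effects below are assumptions.

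**1. Do the methods drop incomplete donors?** Simulated data: 40 subjects, six times, 8 subjects missing only the last value.
- Friedman on all 40, omitting missing values: chi-square 8.375, p = 0.137. This is identical to Friedman on the 32 complete rows.
- A standard repeated-measures ANOVA routine refused the data as unbalanced.
- A mixed model used 40 subjects and 40 × 6 − 8 = 232 readings. Complete rows give 32 × 6 = 192.

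**2. Donors dropped under independent gaps.** With probability p of missing each reading, the share dropped is 1 − (1 − p)^6. The share of recorded readings discarded is 1 − (1 − p)^5.

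| p per reading | Donors dropped | Recorded readings discarded |
|---|---|---|
| 1% | 1 − 0.99^6 = 5.9% | 4.9% |
| 2% | 1 − 0.98^6 = 11.4% | 9.6% |
| 3% | 1 − 0.97^6 = 16.7% | 14.1% |
| 5% | 1 − 0.95^6 = 26.5% (0.2649) | 22.6% |

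For BAI the exponent is 3: 1 − 0.98^3 = 5.9% and 1 − 0.95^3 = 14.3%.

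If a fraction d of donors misses only 48 h, the recorded readings discarded are 5d/(6 − d). For d = 10% this is 0.5/5.9 = 8.5%, although only 0.10/6 = 1.7% of readings are missing.

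**3. Power, as an illustration.** Assume a difference of 0.5 SD, two-sided alpha 0.05 and 63 per arm (80% power with complete data). Power = Φ(0.5·√(n/2) − 1.96), with n the number analysed per arm.
- p = 2%: complete rows n = 63 × 0.886 = 55.8, power 75%. Available data at one time n = 63 × 0.98 = 61.7, power 79%.
- p = 5%: complete rows n = 63 × 0.735 = 46.3, power 67%. Available data at one time n = 63 × 0.95 = 59.9, power 78%.

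**4. Bias if leaving depends on pain.** Assumptions: normal VAS, SD 2 cm, true effect −1.0 cm at every time, equal correlation 0.3 to 0.7 between times, 400,000 donors per arm. Leaving before 48 h depends on the 24 h score and is set so that 10% to 30% of controls leave. The result is the complete-case difference in the mean of the first five readings.
- Probabilistic leaving, odds 1.35 to 2 times higher per cm lower pain: about −0.98 to −0.83 cm. The weakest setting lies between −0.98 and −0.99, depending on the run.
- Worst case, every donor below a fixed 24 h cut-off leaves and nobody above it does: −0.84 to −0.57 cm, with 22% to 49% of intervention donors deleted.
- All donors, all recorded readings at the first five times: −1.00 cm in the worst-case scenario.
- At 48 h in the worst case, likelihood-type prediction from the earlier scores gives −0.99 to −1.01 cm, against −0.89 to −0.61 cm for complete cases. Recovery is expected here, because leaving depends only on an observed score (missing at random).

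**The case against.** The strongest reply is that section 8 does not force this loss. VAS is continuous, the objective speaks of predefined times, and a t-test or Mann-Whitney test at each time would keep every earlier score. That stands, and it limits the point to the repeated-measurements route. It does not remove the point: VAS at six times is repeated data, section 8 has a line for repeated data, and nothing assigns VAS to the other tests instead.

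Second, Friedman yields no between-arm difference, so there is none for it to distort. That also stands. The bias argument applies to repeated-measures ANOVA only.

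Third, a reader might infer that donors who recover well leave before 48 h, that the intervention arm therefore loses more donors, and that the trial's effect is being shrunk by up to about 40%. The documents do not support this. They say nothing about discharge, length of stay or missed readings, and they schedule collection by trained staff through 48 h. If donors stay in hospital that long, the loss could be small. The 40% figure (−0.57 against −1.0) also needs an all-or-nothing cut-off; probabilistic leaving gives a much smaller shift.

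Finally, a mixed model is not the only remedy. A stated missing-data rule, or assigning per-time tests to VAS, would also keep the scores.

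**Conclusion.** The point holds in a limited form. If the repeated-measurements line is used for VAS, BAI or postoperative SpO₂, one missing reading drops the donor from that analysis, and the plan has no rule for this. The mechanism is certain; its size here is unknown.

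For six readings, assumed independent gaps of 1% to 5% drop 6% to 26% of donors. That is a loss of power, not a bias. Bias needs missingness related to pain, which is an assumption with no support either way in the documents. Given that assumption, the plausible shift is from −1.0 to about −0.98 to −0.83 cm, and the −0.84 to −0.57 cm range should be read only as a worst case.

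The deletion is separate from the per-protocol rule, although that undefined rule could remove the same donors again. The change is worth making because it is cheap and also supplies the between-arm comparison that Friedman cannot give.

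**What to change.** In section 8, for the between-arm comparison of VAS, BAI and postoperative SpO₂:
- Replace repeated-measures ANOVA or Friedman with a linear mixed model. Fixed effects: arm, time as a category, and arm by time. Covariance: unstructured, with compound symmetry only if the unstructured model does not converge.
- Use every recorded reading from each donor in the analysis set.
- State that a missing reading does not by itself remove a donor under the per-protocol line.
- Report the number of readings by time and arm.
- Keep Mann-Whitney tests at each time as a sensitivity analysis for skewed or ceiling-limited scores.

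The cost is SAP wording and, if the analysis has been run, a re-analysis. No new data are needed. SPSS has a mixed-model procedure; its availability in the named version should be confirmed. The planned completion date is November 2024, so if outcome data have already been seen, the change should be dated and reported as made after that. The model assumes that readings are missing at random given the observed scores and that residuals are approximately normal.

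### Correlations are planned without adjustment for arm; if taken over all donors, a session effect on both variables can inflate or create a coefficient

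*Combined protocol and SAP*

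**What the plan says.** The whole provision for correlations is one line in section 8 (Statistical Analysis Plan): "Correlations: Pearson or Spearman coefficients". The same section sets a general significance threshold of 0.05. It gives no variable pairs, no time points, no statement of pooled or within-arm calculation, and no partial, stratified or regression-based version. No objective in section 2 and no outcome in section 6 names a correlation.

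Three other places bear on how the line would be used:

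- Section 1 (Background and Rationale) states: "Preoperative anxiety has been shown to negatively affect postoperative pain, hemodynamic stability, anesthetic requirements, and overall recovery". This makes anxiety and pain, or anxiety and hemodynamics, plausible pairs, although the plan does not name them.
- Section 6 (Outcome Measures) schedules the Beck Anxiety Inventory (BAI) at "30 minutes preoperatively, postoperative 24 hours, postoperative 48 hours" and the pain score (VAS) at "Postoperative 30 minutes, 2 hours, 6 hours, 12 hours, 24 hours, and 48 hours".
- Section 5 (Interventions) places the 15-minute session one hour before surgery.

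**The concern.** The trial tests whether one session changes anxiety, hemodynamics and pain. If it changes two of these, arm is a common cause of both. A coefficient over all donors then mixes two things: the difference between the arms, and the association between donors treated alike. Only the second bears on whether more anxious donors have more pain.

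Given the rationale in section 1, a significant anxiety-pain coefficient would probably be read as support for the mechanism. Part or all of it could simply be the treatment effect seen again from another angle. At stake is the interpretation of a side analysis, not the main result.

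**Working it through.** **Inputs from the documents.** Two arms, randomized; three BAI times; six VAS times; threshold 0.05.

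**Assumptions, because the documents give no figure.** Allocation 1:1 (2:1 as a check); two-sided tests; total N from 40 to 200; standardised arm effects from 0 to 1.5 SD; within-arm correlation zero; normally distributed data. The plan gives no sample size, power or expected correlation, so there is no figure of its own to reproduce.

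**Step 1: can any BAI reading be free of the session?** The session starts about 60 minutes before surgery and lasts 15, so it ends about 45 minutes before. The first BAI is at 30 minutes before. All three BAI readings therefore follow the session, and no earlier one is listed. All 3 × 6 = 18 possible BAI-VAS pairs can carry an arm effect on both sides.

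**Step 2: expected pooled coefficient.** Let p be the share of donors in one arm, v = p(1 − p), and dA and dP the arm effects on anxiety and pain in within-arm SDs. With zero within-arm correlation:

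r = v·dA·dP / √[(1 + v·dA²)(1 + v·dP²)]

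At 1:1, v = 0.25. With dA = dP = d this becomes r = 0.25d² / (1 + 0.25d²):

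- d = 0.2: 0.01/1.01 = 0.01
- d = 0.3: 0.0225/1.0225 = 0.02
- d = 0.5: 0.0625/1.0625 = 0.06
- d = 0.8: 0.16/1.16 = 0.14
- d = 1.0: 0.25/1.25 = 0.20

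At 2:1 the values are slightly smaller: 0.05, 0.125 and 0.18 for d = 0.5, 0.8 and 1.0. If either effect is zero, the numerator and r are zero.

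**Step 3: false-positive rate.** Simulation with 10,000 trials per setting, 1:1 allocation and zero within-arm correlation gave these rejection rates for the pooled Pearson coefficient:

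| Total N (assumed) | 0.5 SD on both | 0.8 SD on both | 1.0 SD on both | 0 and 0.5 SD |
|---|---|---|---|---|
| 40 | 6.3% | 14.1% | 24.8% | 4.8% |
| 60 | 7.2% | 18.5% | 34.6% | 4.6% |
| 100 | 8.8% | 28.6% | 52.4% | 5.4% |
| 200 | 13.4% | 50.4% | 82.2% | 5.0% |

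Pooled Spearman is nearly the same (at N = 100: 8.7%, 28.4% and 53.3% for the three two-sided effects), so using ranks does not help.

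**Step 4: after adjustment for arm.** The partial Pearson coefficient (both variables centred within arm, N − 3 degrees of freedom) rejected in 4.6 to 5.4% of trials in every setting. The simulation error at 5% is √(0.05 × 0.95/10,000) = 0.2 percentage points, so this range agrees with the nominal rate. The partial Spearman version was not simulated. Its expected value is also zero when the variables are unrelated within arms.

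**The case against.** **The pooled analysis is not in the plan.** This stands. The line states neither pooling nor the anxiety-pain pair, and within-arm coefficients would fit it and be free of the problem. A reader might infer that the plan commits to a biased coefficient. The documents do not support that; they leave a sound and a distorted analysis equally open.

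**The distortion is often small.** This also stands. At 0.5 SD on both variables with 60 to 100 donors, more than nine in ten trials would show no significant link. The large rates need 0.8 to 1.0 SD on both variables at once, and nothing in the documents supports effects of that size from one short session. A reader might infer that a working session will produce a false anxiety-pain link. That does not follow.

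**Zero within-arm correlation is the worst case and runs against section 1.** Fair. If the within-arm correlation were 0.3 (assumed), 0.5 SD effects would give (0.3 + 0.0625)/1.0625 = 0.34, a shift of 0.04 in a real association.

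**If the session works through anxiety, the between-arm part is genuine.** This limits the word spurious but does not defeat the point. An effect running through anxiety would also leave a correlation within arms, which the adjusted coefficient keeps. It is true that an adjusted coefficient is still observational and does not prove a mechanism.

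**Adjustment alone leaves 18 BAI-VAS pairs to choose from at 0.05.** Correct, so the pairs and times must be named as well.

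**Conclusion.** The point holds in conditional form, as a minor improvement. The plan specifies plain coefficients without an arm term and leaves pairing, timing and pooling open. If they are pooled, an arm effect on both variables can inflate a coefficient or create one. With zero within-arm correlation, the distortion runs from negligible (expected r of 0.01 to 0.02 at 0.2 to 0.3 SD) to material (0.20 at 1.0 SD, with roughly a third to a half of trials falsely significant at 60 to 100 donors). It vanishes if the session shifts only one of the two variables. Every sample size, effect size and allocation ratio behind these figures is an assumption.

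A reader might also infer that the trial's treatment comparisons are compromised. They are not: the primary VAS comparison and the between-arm secondary comparisons do not use these coefficients, and no stated objective depends on them.

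**What to change.** Replace the line in section 8 with:

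> *Correlations: partial Pearson or Spearman coefficients adjusted for randomised arm, for the pairs and time points listed here; unadjusted coefficients pooled over arms will not be interpreted, and the adjusted coefficients are exploratory and observational.*

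The sponsor then lists the pairs and times beneath it.

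The cost is one degree of freedom per coefficient (N − 3 in place of N − 2) and a line of text. No new data are needed. The downside is that coefficients will be somewhat smaller than pooled ones if the session works, because the between-arm part is removed.

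### All eight secondary outcomes share one unadjusted 0.05 threshold with no hierarchy or exploratory label, so a chance finding on anxiety or hemodynamics could be reported as an effect

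*Combined protocol and SAP*

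**What the plan says.** Section 8 is a list of tests followed by a single criterion: "Significance threshold: $p < 0.05". It contains no multiplicity adjustment, testing order, gate on the primary outcome, or statement that secondary results are exploratory.

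Section 6 names one primary outcome, VAS pain, and eight secondary outcomes:

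- Beck Anxiety Inventory (BAI) at three times: "Time Frame: 30 minutes preoperatively, postoperative 24 hours, postoperative 48 hours".
- Postoperative SpO₂ at six times: "Time Frame: Postoperative 30 minutes, 2 hours, 6 hours, 12 hours, 24 hours, 48 hours".
- Intraoperative heart rate, SpO₂, systolic pressure and diastolic pressure, each at three times: "Time Frame: Pre-induction, 30 minutes after induction, 1 hour after induction".
- Opioid consumption.
- Antiemetic use, recorded both as yes/no and in mg.

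Section 1 gives the aim as finding out whether the session "affects perioperative anxiety levels, intraoperative hemodynamics, and postoperative pain outcomes", and the title names the same three areas. One of the secondary objectives in section 2 reads "To compare intraoperative hemodynamic parameters (heart rate, systolic and diastolic blood pressure, SpO₂) between groups".

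For a normally distributed variable section 8 has "Continuous variables with normal distribution: Independent samples t-test", and for a non-normal one Mann-Whitney. For repeated measurements it names repeated-measures ANOVA or Friedman. It does not say whether single time points are also compared between arms.

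**The concern.** Two of the three areas in the stated aim, anxiety and hemodynamics, rest entirely on secondary outcomes. Nothing ranks those outcomes among themselves, says which result decides each area, or limits what may be claimed when pain shows no difference. Hemodynamics alone covers four variables with three readings each. Under a uniform 0.05 criterion, one low p-value in that set could be reported as an effect of the session on hemodynamics, and nothing in the plan would mark it as unprotected.

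The six VAS times of the primary outcome are a separate matter and are not counted here.

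**Working it through.** **Inputs from the documents**

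- Per-test threshold: 0.05 (section 8). Sidedness is not stated; two-sided is assumed.
- Arms: "2 (Intervention vs. Standard Care") (section 3), so each measurement gives one arm contrast.
- Secondary outcomes: 8 (section 6).
- Time-point contrasts: 3 (BAI) + 6 (postoperative SpO₂) + 4 × 3 (intraoperative) = 21.
- Drug outcomes: opioid 1 or 2, and antiemetic 1 to 4, depending on how windows and measures are counted. The total is therefore 23 to 27. One opioid total plus antiemetic yes/no and mg gives 21 + 1 + 2 = 24.
- None of these is a pre-intervention baseline. The session takes place an hour before surgery (section 5), so the BAI half an hour before surgery and the pre-induction readings both follow it.

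**Assumed inputs.** The documents give no correlations. I take 0 to 0.5 between outcomes (rb) and 0.3 to 0.9 between times within an outcome (rw).

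The plan states no family-wise error rate, so there is no figure of its own to reproduce.

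**Step 1. Independent tests.** P(at least one p < 0.05) = 1 − 0.95^k.

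- k = 8: 1 − 0.95^8 = 33.7%
- k = 24: 1 − 0.95^24 = 70.8%

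Expected false positives are 8 × 0.05 = 0.4 and 24 × 0.05 = 1.2.

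**Step 2. Correlated tests.** For outcome i and time j, null statistics were simulated as Z = √rb·G + √(rw − rb)·O_i + √(1 − rw)·E_ij, where G, O_i and E_ij are independent standard normals. A test rejects when |Z| > 1.96.

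| Tests | Between outcomes | Within outcome | P(at least one) |
|---|---|---|---|
| 8, one per outcome | 0 | – | 34% |
| 8, one per outcome | 0.5 | – | 25% |
| 24 time points | 0 | 0.3 | 69% |
| 24 time points | 0 | 0.5 | 65% |
| 24 time points | 0.5 | 0.5 | 46% |
| 24 time points | 0.5 | 0.9 | 36% |

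The drug-window count matters little. At (0.5, 0.9) the result runs from 35.6% with 23 tests to 37.9% with 27. At (0, 0.3) it runs from 67.1% to 72.6%.

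**Step 3. By area.**

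- Hemodynamics, four tests: 1 − 0.95^4 = 18.5% if independent, 15.6% at correlation 0.5.
- Hemodynamics, twelve tests, between-outcome 0.5: 24% (within 0.9) to 32% (within 0.5).
- Anxiety, one test: 5%.
- Anxiety, three tests: 8.4% (within 0.9) to 12.5% (within 0.5).

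**The case against.** **Time-point testing is not stated.** Six of the eight outcomes, supplying 21 of the 24 contrasts, are repeated measurements, and section 8 names repeated-measures methods. A reader might infer that all 24 contrasts are tested one by one; the documents do not say so. This stands, and it is why both counts are given. It does not settle the matter the other way either. Friedman is a within-subject test and does not compare arms. Repeated-measures ANOVA yields a group effect and a group-by-time interaction, and the plan does not say which one counts.

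**The outcomes are already labelled secondary.** Sections 2 and 6 make pain the sole primary outcome, and section 1 speaks of assessing, not of proving. No sentence says that a single p < 0.05 suffices for a claim. That is correct: the fault is that the plan has no rule, not that it has a bad one. The label ranks these outcomes below pain but puts no limit on what may be concluded from them.

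**Each outcome is its own question with its own 5% error.** This is a defensible view of separate outcomes, and it holds for anxiety if there is one test. It does not hold for hemodynamics, where four variables feed one conclusion.

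**Not every objective is an arm comparison.** The section 2 objectives on postoperative oxygen saturation and on drug use do not mention groups. Those outcomes supply 6 + 1 + 2 = 9 of the 24 contrasts. Dropping them leaves five outcomes, and 1 − 0.95^5 = 22.6% with independent single tests (less with positive correlation), still far above 5%.

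**Conclusion.** The concern holds in this form: a uniform unadjusted threshold on eight secondary outcomes, with no hierarchy or exploratory label, in a trial whose title and aim put anxiety and hemodynamics beside pain. The secondary family as a whole and hemodynamics exceed 5% on either reading of the plan; the figures depend on the assumed correlations and on the session affecting none of the outcomes counted.

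Three stronger statements are tempting and are not supported.

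- A reader might join the two readings into a single range for 24 tests. The 25% belongs to eight tests; the assumed correlations give 36-69% for 24, and even 69% is not a ceiling, since independence gives 71%.
- A reader might say that the error rate for anxiety is well above 5%. With one BAI comparison it is exactly 5%; it exceeds that only if the three times are tested separately.
- A reader might say that the plan licenses a claim from any one reading. It is silent, which leaves such a claim open but does not endorse it.

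The primary pain analysis is not affected by this point.

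**What to change.** Add to section 8:

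> Each repeated secondary outcome is compared between arms by one overall group comparison across its time points. All secondary outcomes are exploratory: they are reported as between-arm differences with 95% CIs, without multiplicity adjustment, and an isolated p < 0.05 on an outcome or time point does not support a claim of effect.

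The first sentence settles how many tests there are. The second does not lower the chance of a small p-value, but it stops one from being read as a demonstrated effect.

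A fixed testing order gated on pain would be an alternative, but I do not recommend it here. The documents give no basis for ranking, for example, anxiety ahead of opioid use, and a gate needs one defined primary pain comparison, whereas section 6 lists six VAS times. Section 10 also puts study completion at November 1, 2024. If data have already been seen, an order chosen now would not be prespecified, while an exploratory label can still be applied at reporting.

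**Cost.** Two sentences, with no extra patients or data. Secondary results, including anxiety and hemodynamics, can then be reported only as supportive. One overall BAI comparison also merges the preoperative and postoperative levels, so the estimates at each time should still be shown with their CIs.
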